### 9.5.3. Study Population

Demographics
Age 
 
GSK standard integrated data standards library (IDSL) algorithms will be used for calculating age where birth date will be imputed as follows:                             
 
Any subject with a missing day will have this imputed as day '15'.
 
Any subject with a missing date and month will have this imputed as '30th June'.
 
 
 
Birth Year will be presented in listings as 'YYYY'.
 

Body Mass Index (BMI) 
 
Calculated as Weight (kg) / [Height (m)]
 

Baseline Characteristics
Time since SLE Diagnosis 
 
Calculated as:                             <math display="block">\frac{(Enrollment\ date - Diagnosis\ date + 1)}{365.25}</math> 
 
Partial dates will be imputed as described in Section 9.6.2.1: Handling of Missing and Partial Dates
 
 
 

Exposure Duration 
 
Duration or extent of exposure (days) = (Medication End Date – Medication Start Date) +1                             
 
Last contact Date (as defined in Section 9.5.3) will be used as Medication End Date if medication is ongoing at the time of data cut
 
May be calculated for historical, at baseline and post (follow-up) enrollment
 
For multiple medication records within each medication predefined category (i.e anti-malarial, Mycophenolate Mofetil etc):                                     
 
the start date of earliest and end date of latest medications will be used when there is overlap in days of use
 
total of all durations of exposures will be used when there is no overlap in days of use
 
 
 
 
 

Disposition Duration 
 
Duration since last known visit or last contact date                             
 
Subject who has an 'Ongoing' status on the database (applicable to final analysis dry-run) will be categorized by duration since last contact calculated as: (DataCut Off Date (DCO) – Last Contact Date +1)/365.25
 
The following categories will be used:                                     
 
Last contact date to DCO is < 0.5 year
 
 
 
 
 

 
- Last contact date to DCO is 0.5 - < 1 year
 
- Last contact date to DCO is 1 - < 2 years
 
- Last contact date to DCO is 2 - < 3 years
 
- Last contact date to DCO is 3 - < 4 years
 
- Last contact date to DCO is 4+ years
 

 
• Last contact date definition:             
 
○ maximum (death date [supersedes all other dates], last data assessment date, last visit date, last AE or hospitalization date)
 
○ in the case that the above date is greater than the reference end date (date of completion or withdrawal from end of study disposition CRF page), then the last contact date will be replaced with the reference end date. This is equivalent to the risk end period for each subject, and will be used for the subject-years calculations.
 
 
 

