#### 5.6. Examination of Covariates, Other Strata and Subgroups

##### 5.6.1. Covariates and Other Strata

The list of potential confounding factors included in statistical analysis to minimize selection and confounding bias will be listed in Appendix 9.9.

Descriptive summary will be performed for the subject demographic characteristics and some other covariates:

- i. Baseline SDI (0 vs  $\geq 1$ )
- ii. Hospitalization within 6 months prior to study enrollment (Yes vs No)
- iii. SLEDAI 2000 score at baseline ( $<10$  vs  $\geq 10$ )
- iv. Baseline Immunosuppressant use (Yes vs No; mycophenolate vs immunosuppressant other than mycophenolate)
- v. Duration of prior/baseline medication (i.e. Immunosuppressants, anti-malarials or other) ( $<1$ , 1-2 or  $>2$ years)
- vi. SLE diagnosis duration ( $<1$ , 1- $<5$ , 5- $<10$ , 10- $<15$ , 15- $<20$   $\geq 20$ years)
- vii. Oral corticosteroids dose (mg/day) use at baseline (Always  $<7.5$ mg/day,  $\geq 7.5$ mg/day for  $\leq 2$  weeks or  $\geq 7.5$ mg/day for  $> 2$  weeks)
- viii. Region (US/Canada vs Europe vs Other)
- ix. Race (Black, White, Asian, Other)
- x. Positive anti-dsDNA at baseline
- xi. Low complement at baseline

For the elderly population, sub-group summary will be performed as part of the end of study reporting (to fulfil the Elderly analysis post-approval commitment). Any analysis for elderly sub-group will be restricted to subjects aged 65 yrs and older, grouped as  $\geq 65$  years and age  $\geq 75$  years if feasible.

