**7.1.5.2. Statistical Methodology Specification related to study withdrawal event**

Endpoint / Variables

 
• Study Withdrawal event
 

Endpoint Specification

1. The percentage of subjects withdrawing from the study at the time of the final analysis data cut will be calculated for each exposure group, using the Kaplan-Meier product-limit estimator for the survival probability (the probability of not withdrawing from the study), as follows:
 $\hat{S}(t) = \prod_{t_i \leq t} \left(1 - \frac{d_i}{n_i}\right)$ 
 
- <math>t_i</math> is the specific time of interest when at least one event occurred
 
- <math>d_i</math> is the number of dropout events at time <math>t_i</math>.
 
- <math>n_i</math> is the number of subjects at-risk up to time <math>t_i</math>.
 
 
2. Withdrawal rates at time <math>t</math> will be computed at time <math>t</math>, denoted as <math>\hat{F}(t)</math>:
 $\hat{F}(t) = 1 - \hat{S}(t)$ 
The probabilities of survival and study withdrawal will be expressed in percentage (%), along with 95% CI, for the following time points: 12, 24, 36, 48, 60 months. Additionally the cumulative number of withdrawals will be presented, along with percentage (calculated as cumulative number of withdrawals/N).
 
For the following time periods: 0-12, 12-24, 24-36, 36-48, 48-60 months, the number at-risk at the start of each time period, along with number of withdrawals during each time period will be presented. Percentage is calculated as <number of withdrawals during time point> / <the number at risk at the start of time period>

Model Checking & Diagnostics

 
• No model-based statistical analysis will be performed; hence there is no model checking and diagnostics to be conducted.
 

Results Presentation

The mock-shell tables showing details of data displays are presented in Appendix 12.

Subgroup Analyses

This analysis may be conducted overall and for each study cohort separately (Current Users and Treatment Initiators; Section 5.6.2) and by relevant clinical covariate listed in Section 5.6.1. The list of TLF Data Displays is presented in Appendix 11.

Sensitivity Analyses

N/A

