## 7.2. Effectiveness Analyses

Overview of planned selected effectiveness measures is shown in Table 3. The analyses will be conducted using ‘Evaluable’ analysis population and by study exposure defined using the ‘Initial Exposure’ strategy (see section 9.2.1.1) and/or by strata of clinical covariates listed in Section 5.6.1. Appendix 11: List of TLF Data Displays provides details of the analyses to be conducted.

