**9.11.3. Effectiveness Endpoints Tables**

Effectiveness Endpoints Tables			
Table No	Analysis Population	Title	Programming Note
SLICC/ACR Damage Index (SDI)			
11.000	Eligible	Summary of Baseline SLICC/ACR Damage Index (SDI)	
11.100	Evaluable	Change from Baseline in SLICC/ACR Damage Index (SDI) by Visit [Initial Exposure – ITT Strategy]	
Hospitalizations			
13.000	Eligible	Summary of Hospitalizations at Baseline by Study Cohort	
13.110	Evaluable	Summary of Hospitalizations Rate by Time Period [Initial Exposure – ITT Strategy]	
13.210	Evaluable	Summary of Hospitalizations Rate by Time Period [While On Initial Exposure Strategy]	
13.310	Evaluable	Summary of Hospitalizations Rate by Time Period [As-Exposed – Time Varying Strategy with 14 Weeks Risk Window]	
SLE Medications			
14.000	Eligible	Duration of Prior SLE Medications Not in Use at Baseline (Historical) by Study Cohort	
14.100	Eligible	Duration of Prior SLE Medications in Use at Baseline by Study Cohort	
14.200	Eligible	Frequency of Prior SLE Medications in Use at Baseline by Study Cohort	
14.300	Eligible	Frequency of Concomitant SLE Medications by Study Cohort	
Corticosteroids Use			
15.000	Eligible	Summary of Corticosteroids Usage at Baseline	
15.101	Evaluable	Change from Baseline in Average Corticosteroids Dose by Visit [Initial Exposure – ITT Strategy]	
15.201	Evaluable	Summary of Corticosteroids Usage by Visit [Initial Exposure – ITT Strategy]	

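### SAP 9.5.3 does not stop the exposure-duration clock at enrollment, so for drugs in use at baseline that continue, follow-up time is counted as prior treatment

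*SAP*

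**What the plan says.** SAP 9.5.3, under its Baseline Characteristics block, has the plan's only derivation of medication duration: "Duration or extent of exposure (days) = (Medication End Date – Medication Start Date) +1". For continuing drugs, the last contact date "will be used as Medication End Date if medication is ongoing at the time of data cut". The section adds "May be calculated for historical, at baseline and post (follow-up) enrollment", without a cut-point for any of the three. For several records in one drug category, "the start date of earliest and end date of latest medications will be used when there is overlap in days of use"; durations are summed when records do not overlap.

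The result feeds two baseline items:
- SAP 5.6.1, covariate v, in bands <1, 1-2 and >2 years: "Duration of prior/baseline medication (i.e. Immunosuppressants, anti-malarials or other".
- Table 14.100 in SAP 9.11.3: "Duration of Prior SLE Medications in Use at Baseline by Study Cohort".

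The 5.6.1 covariates may also define strata. SAP 7.1.5.2 lets the withdrawal analysis be run "by relevant clinical covariate listed in Section 5.6.1", and SAP 7.2 lets effectiveness be analysed "by strata of clinical covariates listed in Section 5.6.1".

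Apart from the special rule for Benlysta interruptions, SAP 9.5.2 defines a baseline medication as one whose end date is on or after enrollment.

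**The concern.** A baseline covariate should be fixed by what is known at enrollment. Here, for any drug in use at Day 1 that continues, the formula runs on to the stop date or to last contact. The value then mixes treatment before entry with persistence on the drug and length of follow-up afterwards. The item directly above it in SAP 9.5.3, time since SLE diagnosis, is explicitly anchored at the enrollment date; exposure duration is not.

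This matters because protocol section 1.3 names background treatment as a possible confounder, and protocol section 8.3.2 wants initiators compared with patients of similar treatment history. Table 14.100 is the listed display of how long drugs in use at baseline had been taken. If withdrawal were stratified by covariate v, the strata would be partly defined by the outcome.

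**Working it through.** **Inputs.** Drop-out of 10% per year and 5 years of follow-up (protocol section 8.2); target study days 183, 366, 731 and 1827 (SAP 5.3); an initiator's qualifying drug started fewer than 62 days before Day 1 (SAP 5.6.2). Drug-stopping hazards are not in the documents. They are assumed to be 0, 0.1, 0.2 and 0.4 per year.

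**Check of the drop-out model.** Mean follow-up per patient is (1 − 0.9^5)/(−ln 0.9) = 0.40951/0.10536 = 3.887 years. Times 2,000 this is 7,773.5 patient-years, and times 1,000 it is 3,886.8. These agree with the protocol's 7,773 and 3,886. The same 3.89 years is the average follow-up that the rule adds to a baseline drug that is never stopped.

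**One patient.** A drug starts 30 days before Day 1 and is still ongoing at last contact on study day d. The SAP formula gives (30 + d)/365.25 years. Cut at enrollment it is 31/365.25 = 0.08 years, band <1, whatever d is.

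| Last contact (study day) | SAP formula | Years | Band |
|---|---|---|---|
| 183 | 213/365.25 | 0.58 | <1 |
| 366 | 396/365.25 | 1.08 | 1-2 |
| 731 | 761/365.25 | 2.08 | >2 |
| 1827 | 1857/365.25 | 5.08 | >2 |

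Current users can move too. A drug started 500 days before Day 1 is 501/365.25 = 1.37 years at enrollment (band 1-2), but 866/365.25 = 2.37 years (band >2) if last contact is day 366. A drug already taken for more than 2 years keeps its band, though its continuous duration is still inflated.

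**Share of initiators in the >2 band, for the qualifying drug.** With a start 30 days before Day 1, the drug and the follow-up must both last a further 2 − 30/365.25 = 1.918 years. The share is exp[−(0.10536 + h) × 1.918], where h is the stopping hazard.

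| h per year | Share in >2 band | Share if cut at enrollment |
|---|---|---|
| 0 | 82% | 0% |
| 0.1 | 67% | 0% |
| 0.2 | 56% | 0% |
| 0.4 | 38% | 0% |

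With h = 0, moving the start date across 0 to 61 days before Day 1 changes the share only from 81.0% to 82.4%.

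**Link to withdrawal.** An initiator who leaves within a year of entry has at most about (61 + 366)/365.25 = 1.17 years on the qualifying drug, and so cannot reach the >2 band. In a withdrawal analysis of that drug by duration band, early withdrawal among initiators in the top band would be zero by construction.

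**The case against.** The best reply is that the plan already implies separate durations. SAP 9.5.3 names historical, baseline and follow-up versions, SAP 9.5.2 divides study phases at enrollment, and the title of Table 14.100 refers to prior use. On that reading the last-contact rule belongs to the follow-up version only. This may well be the intent, and the mock shells, kept in a separate file, might confirm it. But the SAP gives no cut-point, and its medication phases classify whole records rather than splitting time: a drug that continues past Day 1 meets both the baseline and the post-baseline definitions. A programmer following the text would compute start to end.

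Several stronger readings are tempting but not supported:
- **That no initiator can properly appear in the >2 band of Table 14.100.** Initiator status rests on Benlysta or, for comparison patients on several drugs, the most recently added immunosuppressant (SAP 5.6.2). The table and covariate v cover other drugs as well, which an initiator may truly have taken for years. The 0% holds for the qualifying drug only.
- **That the multiple-record rule counts gaps between courses as exposure.** The two clauses can be read together as merging overlapping records and adding separate ones, which is the union of the intervals. The text could be clearer, but an error is not shown.
- **That distorted stratified outcome results are planned.** Such strata are optional in SAP 7.1.5.2 and 7.2, and no outcome table in Appendix 11 is listed by this covariate.
- **That treatment history cannot be compared at all.** Table 14.000 (historical drugs) and Table 14.200 (frequency of drugs in use at baseline) do not have this fault.

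**Conclusion.** The point stands in a limited form. As written, SAP 9.5.3 gives a wrong baseline value for every drug in use at enrollment that continues afterwards. The direction needs no assumption; the 67%, 56% and 38% shares rest on assumed stopping hazards and on the planned drop-out rate. Whether the inflation differs between the Benlysta and comparison groups depends on persistence, which the documents do not give.

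The effect reaches Table 14.100, the three-band covariate v, and any optional withdrawal or effectiveness strata built on it. A reader might infer that the safety comparison is compromised. It is not: medication duration is absent from the propensity score covariates (SAP Appendix 9, Table 4), the initiator/current-user split uses start dates only, and neither the AESI rates nor their weights use the variable. Durations of historical drugs, which ended before enrollment, are also unaffected.

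**What to change.** In SAP 9.5.3, define duration for baseline medications as min(Medication End Date, Enrollment Date) − Medication Start Date + 1. Set it to 0 for drugs started on Days 2 to 4, which SAP 5.2 counts as baseline and for which the formula would give 0, −1 or −2. Use this version for Table 14.100 and covariate v, and keep the present start-to-end formula with the last-contact rule for follow-up exposure only. As a minor clarification, state that multiple records in a category are combined as the union of their intervals.

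The cost is a few lines of SAP text and a small programming change. No new data are needed, since start dates, end dates and enrollment dates are already collected.

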**9.5.4. Safety**

Adverse Events of Special Interest

 
• Duration of AESI (days) = Date of AESI resolution – AESI start date + 1 (If the AE is ongoing the duration will be left blank and no imputation will be done)
 

**9.5.5. Effectiveness**

Effectiveness endpoints	
SLICC/ACR Damage Index (SDI) score	

 
• SDI is designed to capture items of irreversible organ damage (present for at least 6 months) occurring in subjects with SLE. It consists of 12 organ system (listed below) scales each having subscales comprised of up to six components.
 
• Scoring will be performed for the following items as per Systemic Lupus International Collaborating Clinics/American College of Rheumatology Damage Index.
 
• Total scores used for analysis will not be obtained directly from the eCRF electronic data capture (EDC), but instead calculated by summing the scores of each domain.
 
• If any item is missing, the total score should be set to missing (see Section 9.6.2.3 for exceptions).
 
	
Item	Score
Ocular (either eye, by clinical assessment)	
Any cataract ever	0,1
Retinal change or optic atrophy	0,1
Neuropsychiatric	
Cognitive impairment (e.g. memory deficit, difficulty with calculation, poor concentration, difficulty in spoken or written language, impaired performance levels) or major psychosis	0,1
Seizures requiring therapy for 6 months	0,1
Cerebrovascular accident ever (score 2 if >1)	0,1,2
Cranial or peripheral neuropathy (excluding optic)	0,1
Transverse myelitis	0,1
Renal	
Estimated or measured glomerular filtration rate <50%	0,1
Proteinuria >3.5 g/24hours	0,1
Or	

Effectiveness endpoints	
End-stage renal disease (regardless of dialysis or transplantation)	0,3
Pulmonary	
Pulmonary hypertension (right ventricular prominence, or loud P2)	0,1
Pulmonary fibrosis (physical and radiograph)	0,1
Shrinking lung (radiograph)	0,1
Pleural fibrosis (radiograph)	0,1
Pulmonary infarction (radiograph)	0,1
Cardiovascular	
Angina or coronary artery bypass	0,1
Myocardial infarction ever (score 2 if >1)	0,1,2
Cardiomyopathy (ventricular dysfunction)	0,1
Valvular disease (diastolic, murmur, or systolic murmur >3/6)	0,1
Pericarditis for 6 months, or pericardiectomy	0,1
Peripheral vascular	
Claudication for 6 months	0,1
Minor tissue loss (pulp space)	0,1
Significant tissue loss ever (e.g. loss of digit or limb) (score 2 if >1 site)	0,1,2
Venous thrombosis with swelling, ulceration, or venous stasis	0,1
Gastrointestinal	
Infarction or resection of bowel below duodenum, spleen, liver, or gall bladder ever, for any cause (score 2 if >1 site)	0,1,2
Mesenteric insufficiency	0,1
Chronic peritonitis	0,1
Stricture or upper gastrointestinal tract surgery ever	0,1
Musculoskeletal	
Muscle atrophy or weakness	0,1
Deforming or erosive arthritis (including reducible deformities, excluding avascular necrosis)	0,1
Osteoporosis with fracture or vertebral collapse (excluding avascular necrosis)	0,1
Avascular necrosis (score 2 if >1)	0,1,2
Osteomyelitis	0,1
Skin	
Scarring chronic alopecia	0,1
Extensive scarring or panniculum other than scalp and pulp space	0,1
Skin ulceration (excluding thrombosis) for >6 months	0,1
Premature gonadal failure	0,1
Diabetes (regardless of treatment)	0,1
Malignancy (exclude dysplasia) (score 2 if >1 site)	0,1,2

From the Systemic Lupus International Collaborating Clinics (SLICC) and the American College of Rheumatology Diagnostic and Therapeutic Criteria Committee, 1996 (Gladman, 1996)

Effectiveness endpoints		
SLEDAI, 2000 (S2K) score		

 
Assessments consist of 24 individual items (listed below) in which signs and symptoms, laboratory tests, and physician's assessment for each of 9 organ systems are given a weighted score and summed if present (marked 'Yes') at the time of the visit or <math>\pm 30</math> days of enrollment visit.
 
The maximum theoretical score is 105 (all 24 descriptors present simultaneously) with 0 indicating inactive disease (marked 'No'), but in practice few subjects have scores >45.
 
Total Scores used for analysis are derived based on the sum of the weighted value for each organ system component (see Gladman, 2002).
 
		
Descriptor	Weight	Definition
Seizure	8	Recent onset, exclude metabolic, infectious or drug cause.
Psychosis	8	Altered ability to function in normal activity due to severe disturbance in the perception of reality. Include hallucinations, incoherence, marked loose associations, impoverished thought content, marked illogical thinking, bizarre, disorganized, or catatonic behavior. Exclude uremia and drug causes.
Organic Brain Syndrome	8	Altered mental function with impaired orientation, memory or other intellectual function with rapid onset and fluctuating clinical features. Include clouding of consciousness with reduced capacity to focus and inability to sustain attention to environment, plus at least 2 of the following: perceptual disturbance, incoherent speech, insomnia or daytime drowsiness, or increased or decreased psychomotor activity. Exclude metabolic, infectious, or drug causes.
Visual Disturbance	8	Retinal changes of SLE. Include cytooid bodies, retinal hemorrhages, serious exudate or hemorrhages in the choroids, or optic neuritis. Exclude hypertension, infection, or drug causes.
Cranial Nerve Disorder	8	New onset of sensory or motor neuropathy involving cranial nerves. Include vertigo due to lupus.
Lupus Headache	8	Severe persistent headache: may be migrainous but must be non-responsive to narcotic analgesia.
CVA	8	New onset of cerebrovascular accident(s). Exclude arteriosclerosis.
Vasculitis	8	Ulceration, gangrene, tender finger nodules, periungual infarction, splinter hemorrhages, or biopsy or angiogram proof of vasculitis.
Arthritis	4	$\geq 2$ joints with pain and signs of inflammation (i.e., tenderness, swelling or effusion).
Myositis	4	Proximal muscle aching/weakness associated with elevated creatine phosphokinase/aldolase or electromyogram changes or a biopsy showing myositis.
Urinary Casts	4	Heme-granular or red blood cell casts.
Hematuria	4	>5 red blood cells/high power field. Exclude stone, infection, or other causes.
Proteinuria	4	>0.5 gm/24 hours.
Pyuria	4	>5 white blood cells/high power field. Exclude infection.
Rash	2	Inflammatory type rash.
Alopecia	2	Abnormal, patchy or diffuse loss of hair.
Mucosal Ulcers	2	Oral or nasal ulcerations.
Pleurisy	2	Pleuritic chest pain with pleural rub or effusion, or pleural thickening.
Pericarditis	2	Pericardial pain with at least one of the following: rub, effusion or electrocardiogram or echocardiogram confirmation.
Low Complement	2	Decrease in CH50, C3, or C4 below the lower limit of normal for testing laboratory.
Increased DNA Binding	2	Increased DNA binding by FARR assay above normal range for testing laboratory.

Effectiveness endpoints		
Fever (move to hematologic)	1	>38 degrees C (38°C). Exclude infectious cause.
Thrombocytopenia	1	<100,000 platelets/mm  , exclude drug causes.
Leukopenia	1	<3,000 white blood cells/mm  , exclude drug causes.

Adapted from: Gladman D Dafna, Ibañez Dominique and Urowitz B Murray. Systemic lupus erythematosus disease activity index 2000. J Rheumatol 2002;29:288-29 [Gladman, 2002]

## 9.6. Appendix 6: Reporting Standards for Missing Data

### 9.6.1. Study Withdrawals

Element	Reporting Detail
General	
 
Subject study completion (i.e. as specified in the protocol) was defined as completion of the 5-year follow-up following enrollment into study.
 
Withdrawn subjects will not be replaced in the study. Subjects who develop AESI will still remain in the study except for fatality event, withdrawal of consent or withdrawal at physician discretion.
 
All available data from subjects who were withdrawn from the study will be listed and all available data will be included in summary Tables and Figures.
 

